6.4 Study Intervention Compliance

Participants will be observed at the time of dosing by a member of the clinical research team who is licensed and authorized to administer study product (PI, sub-investigator or delegated clinicians) listed on Form FDA 1572. Each dose of study product will be administered by a member of the clinical research team that is delegated to administer the study product.

Study product administration date and time will be documented on site source document and recorded on the appropriate electronic Case Report Form (eCRF).

6.5 Concomitant Therapy

For this protocol, a prescription medication is defined as a medication that can be prescribed only by a properly authorized/licensed clinician. Medications to be reported in the Case Report Form (CRF) are concomitant prescription medications, and supplements.

Information about prior medications, including hormonal contraceptives, taken by the participant in the 30 days prior to initiation of dosing with study product(s) will be recorded on the appropriate CRF.

Concomitant medications include all medications (prescription and OTC medications, supplements, and vaccines), except study products, taken by the participant from the time of the first dose of study product(s) to the end of the study. At each study visit following dosing, including telephone calls, participants will be queried about new ConMeds and changes to existing medications. The following medications are prohibited during the study:

- No medications are allowed after enrollment until completion of all study assessments with the exception of up to 1,000 mg acetaminophen daily for up to 3 days for the relief of common, temporary symptoms (headache, musculoskeletal pain, etc.) if approved by the site PI or authorized clinician.
- Any medications known to be strongly metabolized by CYP3A4 or CYP2D6, or strongly inhibit or induce these enzymes might interfere with the evaluation of the investigational product and should not be used by the participant for 14 days or 5 half-lives of the drug, whichever is longer, prior to and during the study. (See [Appendix C](#) for a partial list).
- Participant should refrain from OTC supplements, such as vitamins and herbal supplements (e.g., Saint John's Wort), for 14 days or 5 half-lives of the supplement, whichever is longer, prior to and for the duration of the trial.

In the event medical conditions dictate the use of medications during the in-patient period, appropriate treatment may be prescribed by authorized/licensed clinician. For events during the out-patient period, participants are encouraged to notify the investigator or, if they seek care by their personal healthcare provider, to comply with the course of therapy as prescribed and inform the study investigator as soon as practical.

Any drug or vaccine used or received by the participant during the trial should be recorded on the appropriate CRF.

For additional lifestyle restrictions, see [Section 5.4](#).

6.5.1 Rescue Medicine

Not Applicable.

6.5.2 Non-Research Standard of Care

If at any time during the inpatient facility stay, the participant develops illness requiring medical care that is beyond the care available in this facility, the participant will be transferred to a hospital capable of providing this level of care. The hospital and physicians accepting the participant for care will be informed of the participant's participation in this research study so that the participant can be managed according to appropriate precautions per standard of care.

7. STUDY INTERVENTION DISCONTINUATION AND PARTICIPANT DISCONTINUATION/WITHDRAWAL

7.1 Halting Criteria and Discontinuation of Study Intervention

7.1.1 Study Halting Criteria

Cohort Halting Rules

If any of the following criteria occur, dosing of subsequent participants in the cohort will be halted and could resume after blinded review by the SMC at an *ad hoc* meeting:

- One participant experiences a treatment-related SAE assessed as related to the investigational study product, with the exception of accidental injury.
- One participant experiences a treatment-related Grade 3 or higher adverse event.
- Two or more participants experience a Grade 2 or higher systemic AE in the same higher level group term (HLGT) per MedDRA classification assessed as related to the study product.
- One participant develops QT prolongation on a post dose ECG, defined as a QT interval with Fridericia correction method (QTcF) > 500 msec (Grade 3).
- One participant develops clinically significant abnormal liver function tests as follows:
 - ALT and/or AST $> 5 \times$ upper limit of normal (ULN) in the absence of a total bilirubin increase.
 - ALT and/or AST elevations $> 3 \times$ ULN in the presence of a total bilirubin increase $> 2 \times$ ULN or an international normalized ratio (INR) > 1.5 without findings of cholestasis or other alternate etiology to explain the elevations (i.e., "Hy's Law cases").
 - Symptomatic ALT and/or AST elevations $> 3 \times$ ULN with the appearance of fatigue, nausea, vomiting, right upper quadrant pain or tenderness, fever, rash and/or eosinophilia ($> 5\%$ of total WBC count).

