7.1.2 Individual Halting Criteria

A participant will be discontinued from further dosing and the cohort dosing will be stopped for the SRC review or SMC *ad hoc* meeting if any of the following criteria are met:

- A participant experiences an SAE, regardless of the relationship to the study product, with the exception of accidental injury.
- A participant experiences clinically significant Grade 3 or higher AE (laboratory or systemic) assessed as related to the study product.
- A participant develops anaphylaxis within 24 hours after receiving the study product.
- A participant experiences a suspected drug-related hypersensitivity AE Grade 2 or higher.
- A participant develops QT prolongation on a post dose ECG, defined as a QT interval with QTcF > 500 msec (Grade 3).
- In the opinion of the PI, further dosing would not be in the best interest of the participant.

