8.5.4 Classification of an Adverse Event

The determination of seriousness, severity, and causality will be made by an on-site investigator who is qualified (licensed) to diagnose AE information, provide a medical evaluation of AEs, and classify AEs based upon medical judgment.

Severity of Event

All AEs or SAEs will be assessed for severity, according to the FDA Toxicity Grading Scale for Healthy Adult and Adolescent Volunteers Enrolled in Preventive Vaccine Clinical Trials, available at <https://www.fda.gov/media/73679/download>, and supplemental grading parameters are included in [Appendix A](#). If the severity of any AE changes, the highest severity should be recorded.

Relationship to Study Intervention

For each reported adverse event or reaction, the PI or designee must assess the relationship of the event to the study product using the following guideline:

Related – The AE is known to occur with the study intervention, there is a reasonable possibility that the study intervention caused the AE, or there is a temporal relationship between the study intervention and event. Reasonable possibility means that there is evidence to suggest a causal relationship between the study intervention and the AE. For scale of relatedness, “possibly related”, “probably related”, and “definitely related” map to “related”. Adverse Events when alternative etiology is not identified will be assessed as “related” to the study product.

Not Related – There is not a reasonable possibility that the administration of the study intervention caused the event, there is no temporal relationship between the study intervention and event onset, or an alternate etiology has been established.

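### Liver bullet 1 of Protocol 7.1.1 lapses once bilirubin rises, and bullets 2 and 3 do not catch every such case; other rules close most of the gap

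*Protocol*

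**What the plan says.** Protocol 7.1.1 introduces the liver rules with "One participant develops clinically significant abnormal liver function tests as follows", so all three need a judgement of clinical significance.

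- **Bullet 1:** ALT and/or AST above five times the "upper limit of normal (ULN) in the absence of a total bilirubin increase". No size of increase is given, and there is no causality test.
- **Bullet 2:** above 3 x ULN with bilirubin above 2 x ULN or INR above 1.5, "without findings of cholestasis or other alternate etiology to explain the elevations" (labelled as Hy's Law cases).
- **Bullet 3:** above 3 x ULN with listed symptoms and/or eosinophilia above 5%.

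Other rules bear on the same events:

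- 7.1.1 also halts for one treatment-related event of Grade 3 or higher.
- 7.1.2 stops the participant and the cohort for any SAE except accidental injury, and for this: "A participant experiences clinically significant Grade 3 or higher AE (laboratory or systemic) assessed as related to the study product". It also has a discretionary rule: "In the opinion of the PI, further dosing would not be in the best interest of the participant". It names the QTcF trigger but no liver trigger.
- 8.3.3 makes abnormal post-treatment laboratory values adverse events.
- 8.5.4 calls an event related if, among other grounds, "there is a temporal relationship between the study intervention and event". It adds a default: "Adverse Events when alternative etiology is not identified will be assessed as" related. Its definition of not related ends "or an alternate etiology has been established".
- 8.5.2 says that Grade 4 does not by itself make an event life-threatening.
- 8.5.9 makes Grade 3 or higher liver tests an AESI, which means expedited reporting and SMC discussion rather than a halt.

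**The concern.** Raised bilirubin on top of raised transaminases is the worse liver picture, yet on the literal wording it removes a named trigger. Bullet 1 halts whatever the cause. Once bilirubin rises, an asymptomatic case must instead satisfy bullet 2, which has a higher bilirubin bar and excludes cholestasis and other causes. Two situations can fall between the bullets: (a) bilirubin above 1 and up to 2 x ULN with INR no higher than 1.5; and (b) raised bilirubin with cholestasis or an alternate etiology.

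Protocol 2.3.1 identifies the liver as the target organ in the toxicology program, so these rules should not depend on a favourable interpretation. At stake is whether a pause for SMC review follows from a stated rule or from someone's discretion.

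**Working it through.** The documents give no figure to reproduce; this is a check of rule logic.

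**Grid.** Fix ALT/AST above 5 x ULN and assume clinical significance. Cross bilirubin (normal; >1 to 2 x ULN; >2 x ULN), INR (<=1.5; >1.5), symptoms or eosinophilia (no; yes) and etiology (nothing found; cholestasis only; other cause): 3 x 2 x 2 x 3 = 36 combinations, 24 of them with raised bilirubin.

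**Rules, plain reading.** B1 = bilirubin normal. B2 = (bilirubin >2 x ULN or INR >1.5) and neither cholestasis nor other cause. B3 = symptoms or eosinophilia.

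**Misses, plain reading.** B3 catches every symptomatic combination, so only asymptomatic ones can be missed.
- Normal bilirubin: 0 of 12.
- >1 to 2 x ULN: at INR <=1.5 all 3 etiologies are missed; at INR >1.5 cholestasis and other cause are missed. 3 + 2 = 5 of 12.
- >2 x ULN: cholestasis and other cause are missed at each INR level. 2 x 2 = 4 of 12.
- Total with raised bilirubin: 5 + 4 = 9 of 24.

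**Other readings.** Increase in bullet 1 might mean above 2 x ULN, as in bullet 2; then the middle band meets B1. Or the cholestasis/other-cause condition might attach to INR only; then every combination above 2 x ULN meets B2.

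| Reading | Missed, >1 to 2 x ULN | Missed, >2 x ULN | Total of 24 | Of which other cause |
|---|---|---|---|---|
| Plain | 5 | 4 | 9 | 2 + 2 = 4 |
| Increase means >2 x ULN | 0 | 4 | 4 | 2 |
| Condition on INR only | 5 | 0 | 5 | 2 |
| Both | 0 | 0 | 0 | 0 |

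**After the other rules.** If values above 5 x ULN are Grade 3 or higher, every missed combination without an established other cause defaults to related under 8.5.4 and halts. This leaves the last column, for non-serious events only: 4 of 24 on the plain reading. If the temporal limb of 8.5.4 decides instead, the residual is 0 of 24 on every reading.

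**Is above 5 x ULN always Grade 3?** The reference ranges are in the MOP, so the ULNs must be inferred. In SAP Table 8, Grade 2 ends at 200 and 275 U/L (ALT, female and male) and at 175 and 250 U/L (AST). These equal 5 x 40, 5 x 55, 5 x 35 and 5 x 50, and the other boundaries fit the same ULNs at about 1.1, 2.5 and 10 times. At those ULNs or higher, above 5 x ULN is always Grade 3 or more. At lower ULNs a narrow window opens. For female ALT:

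- assumed ULN 36: 5 x 36 = 180, so 181-200 U/L is Grade 2
- assumed ULN 38: 191-200 U/L
- assumed ULN 39: 196-200 U/L

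Only inside such a window could the plain-reading residual be larger, at most 9 of 24, and that maximum ignores the bilirubin grade. With liver tests raised, Table 8 starts bilirubin Grade 3 at 2.2 mg/dL. For a bilirubin ULN of 1.1 or more, anything above 2 x ULN is therefore Grade 3 or higher. The figure then falls to 5 + 2 = 7 of 24 if an other cause means not related, or 5 of 24 if the temporal limb decides.

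**Bilirubin in situation (a).** For an assumed ULN of 1.3 to 1.4 mg/dL, 2 x ULN is 2.6 to 2.8 mg/dL, above the 2.4 mg/dL beyond which Table 8 assigns Grade 4. Such a value still halts unless judged not related. For a ULN of 1.0 to 1.2, 2 x ULN does not exceed 2.4.

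**After the fix.** B1 is always met: 0 of 36 missed, on every reading.

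**The case against.** The strongest reply is that two permissible readings together remove the gap. In bullet 2 the exclusion of cholestasis and other causes directly follows the INR condition and may qualify it alone; and increase in bullet 1 may borrow the 2 x ULN threshold of the next line. Both are possible. However, the Hy's Law label and the reference to explaining the elevations fit a condition on the whole of bullet 2, and bullet 1 states no threshold. Either reading alone still leaves misses.

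Second, the residual has other safeguards. The investigator may withdraw a participant for a laboratory abnormality (7.2.1). The SRC reviews data to Day 15 before escalation (4.2, 10.1.6). An ad hoc SMC review can be requested (10.1.6), and the study can be stopped early on safety data (10.1.2). Viral hepatitis, heavy alcohol use and prohibited medications are screened out, and liver tests must be normal at entry. All this stands and makes the case remote, but apart from the scheduled SRC review these are discretionary. The temporal limb of 8.5.4 would close the residual, but the same section lets an established other cause make the event not related, so two assessors could differ.

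Third, not halting for an explained liver event may be deliberate. The amendment log says the fold increases in the first two bullets were revised to align with an FDA guidance, which cannot be checked here. That may defend the exclusion in bullet 2. It does not explain why bullet 1 halts for an explained event when bilirubin is normal but not when it is raised.

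Finally, the counts depend on how the grid is drawn. That is right; they show where the rules fail to meet, not how often.

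**Conclusion.** The defect is real and minor. On the plain reading, bullet 1 ceases to apply with any bilirubin increase and the liver bullets miss 9 of 24 combinations. After the other rules, what remains is mainly a non-serious event judged not related because another cause is established: 4 of 24, or 0 if the temporal limb of 8.5.4 governs. This assumes that clinical significance is met and that values above 5 x ULN are Grade 3 or higher, which Table 8 suggests but the unseen MOP ranges must confirm.

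A reader might infer that the protocol would let dosing continue through drug-induced liver injury with raised bilirubin. The documents do not support that. A related Grade 3 event halts under both 7.1.1 and 7.1.2, any SAE other than accidental injury halts under 7.1.2, and an event with no identified other cause is related by default. Nor is there evidence that the wording affected this trial. SAP 6.2 ties the decision not to proceed to moderate allergic reactions, and SAP 4.1 mentions several halting rules without naming a liver one.

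**What to change.** In Protocol 7.1.1, bullet 1, replace the condition on absent bilirubin with *with or without a total bilirubin increase*, and leave bullets 2 and 3 unchanged. This closes the gap under every reading, still subject to the clinical-significance judgement in the lead-in.

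Preferably, also name the liver trigger in 7.1.2, as is done for QTcF. This second change is a new individual stopping rule, not a wording correction, and should be decided as such.

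The cost is one phrase and one line. No new data are needed, because liver tests are already drawn on Days 2, 4, 6 and 8. The downside is a rare extra pause for SMC review, including for events with a benign other cause. The wording should be compared with the cited FDA guidance before reuse.

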7.1.2 Individual Halting Criteria

A participant will be discontinued from further dosing and the cohort dosing will be stopped for the SRC review or SMC *ad hoc* meeting if any of the following criteria are met:

- A participant experiences an SAE, regardless of the relationship to the study product, with the exception of accidental injury.
- A participant experiences clinically significant Grade 3 or higher AE (laboratory or systemic) assessed as related to the study product.
- A participant develops anaphylaxis within 24 hours after receiving the study product.
- A participant experiences a suspected drug-related hypersensitivity AE Grade 2 or higher.
- A participant develops QT prolongation on a post dose ECG, defined as a QT interval with QTcF > 500 msec (Grade 3).
- In the opinion of the PI, further dosing would not be in the best interest of the participant.

7.1.3 Follow Up for Participants Who Discontinued Study Intervention

Discontinuation from the investigational drug product does not mean discontinuation from the study, and remaining study procedures should be completed as indicated by the study protocol. If a clinically significant finding is identified (including, but not limited to changes from baseline) after enrollment, the PI, sub-investigator, or licensed clinician will determine if any change in participant management is needed. Any new clinically relevant finding will be reported as an AE. All other events will be monitored and collected even when drug administration has been discontinued.

See SOA, Early Termination (ET) ([Section 1.2](#)) for data to be collected at the time of study intervention discontinuation.

7.2 Participant Withdrawal from the Study and Replacement

7.2.1 Participant Withdrawal from the Study

Participants are free to withdraw from participation in the study at any time upon request for any reason.

An investigator may discontinue or withdraw a participant from the study for the following reasons:

- Participant becomes pregnant.
- Study non-compliance that in the opinion of the investigator poses an increased risk (i.e., missing safety labs), or compromises the validity of the data.
- If any clinical, laboratory or ECG abnormality, or other medical condition or situation occurs such that continued participation in the study would not be in the best interest of the participant.
- If the participant met an exclusion criterion for participation in the study (either newly developed or not previously recognized) that precludes further study participation.

- Medical disease or condition, or new clinical finding(s) for which continued participation, in the opinion of the investigator might compromise the safety of the participant, interfere with the participant's successful completion of this study, or interfere with the evaluation of responses.
- Participant lost to follow-up.

Every effort should be made to encourage participants to remain in the study for the duration of their planned outcome assessments. Participants will be educated on the continued scientific importance of their data, even if they discontinue study drug.

Unless the participant withdraws consent, those who discontinue study drug early will remain in the study.

If the participant agrees, every attempt will be made to follow all AEs through resolution (return to baseline) or until defined as stable.

The reason for participant discontinuation or withdrawal from the study, whether the decision was made by investigator or participant, and the extent of the withdrawal (i.e., whether participant withdrew from all components of research study or just the study intervention) will be recorded on the CRF.

The investigator will inform the participant that already collected data will be retained and analyzed for this study even if the participant withdraws from this study. Biospecimens collected for the current study will still be used to analyze the study endpoints.

7.2.2 Participant Replacement

Participants who withdraw or are withdrawn from this study after receiving at least one dose of the study product and prior to Day 9 for reasons not related to TEAEs or study drug intolerance may be replaced, at the recommendation of the Site PI and concurrence by the DMID MO, with a participant who will receive the same treatment as the withdrawn participant, and an effort will be made to also be of the same gender as the participant who is replaced. The SDCC must be contacted prior to enrolling any replacement participants.

7.3 Lost to Follow-Up

A participant will be considered lost to follow-up if he or she is unable to be contacted by the study site staff after three attempts. Extensive effort (i.e., generally three documented contact attempts via telephone calls, e-mail, etc., made on separate occasions) will be made to locate or recall the participant, or at least to determine the participant's health status. These efforts will be documented in the participant's study file.

8. STUDY ASSESSMENTS AND PROCEDURES

8.1 Screening Procedures

There is a small amount of risk to participants who report that they are in good health but have an unknown health problem at the time of screening. Screening assessments can occur up to 28 days before the participant's first treatment (Day 1) and may occur in one or two visits. At the first visit, and prior to any other study-related activities, a delegated staff member at the participating site will provide the participant with detailed study information and will obtain written informed consent.

Individuals will have the opportunity to ask questions. The Site PI or authorized sub-investigator or clinician will also be available to answer questions. The site PI will review and approve eligibility criteria.

Some or all of the following assessments are performed during the Screening visit and confirmed at Check-in (Day -1) to determine eligibility requirements as specified in the inclusion ([Section 5.1](#)) and exclusion criteria ([Section 5.2](#)). Assessments are listed in the SOA ([Section 1.2](#)). Guidelines for documentation will be reported in the study-specific MOP and eCRF Instructions.

8.1.1 Clinical Procedures and Evaluations

- **Demographics:** Demographic information (date of birth, gender, ethnicity, and race) will be recorded on the subject's source documents and eCRF at Screening Visit. Name, address, phone number, and emergency contact information will be documented in the source documents only.
- **Eligibility Review:** A review of study inclusion and exclusion criteria will be completed within 28 days before study drug dosing at the Screening and Check-in (Day -1) visits. Confirmation of eligibility for dosing will be performed before dosing on Day 1.

Screening failures and the reason for failure to meet the study eligibility requirements will be documented in source documents and eCRFs.

- **Medical History (MH):** A review of pertinent MH that may impact study participation will be obtained by direct interview of the subject. The MH will capture current disease processes, past disease processes, history of hospitalization, and history of surgery. Participants will be queried regarding a history of significant medical disorders of the head, eyes, ears, nose, throat (HEENT), mouth, skin, the cardiovascular, respiratory, gastrointestinal, renal, urological, nervous, hematological, lymphatic, endocrine, musculoskeletal and genital/reproductive systems. A history of allergies including allergies to medications, medication history, and history of substance and alcohol abuse will be obtained.

Participants will be queried about a history of orthostatic hypotension, any symptoms associated with position change, syncope or near syncope (i.e., dizziness, fainting), and symptoms related to transition from lying down to standing up (such as fast heart rate, dizziness, or fainting).

The MH will be obtained at Screening Visit and updated on Day -1 (Check-in) and before dosing on Day 1. After start of study drug dosing, any worsening of pre-dosing MH or new symptoms will be evaluated and reported as TEAEs.

- **Concomitant Medications (ConMeds):** Medication history will include prescription medication, including contraceptives, and non-prescription drugs, vitamins, supplements and herbal medication, and recent vaccinations including for COVID-19 used in the recent past, and include medications that are prohibited prior to dosing. (See [Section 6.5](#)).

Medications history will be obtained at Screening, Check-in (Day-1) and updated prior to dosing on Day 1. Medications taken prior to dosing will be recorded as “Prior Medications”.

- **Physical Exam (PE):** A Complete PE - except genital, breast, pelvic and rectal exams - will assess general appearance and the following body systems: (1) eyes; (2) ears, nose, throat; (3) cardiovascular system; (4) respiratory system; (5) gastrointestinal system; (6) dermatologic system; (7) extremities; (8) musculoskeletal system; (9) lymph nodes; and (10) neurological/neurosensory examination.

Any abnormal finding on a screening examination assessment must be assessed as Not Clinically Significant (NCS) or Clinically Significant (CS) by the investigator (PI, sub-investigator, or authorized clinician) listed on Form FDA 1572 and recorded in the source document and eCRF.

A complete PE will be performed at the Screening and Check-in (Day -1) visits.

- **Body Mass Index (BMI):** Consists of weight and height measured while wearing indoor clothing and with shoes off. The BMI is calculated using metric units according to the following formula: $BMI = \text{weight (kg)} / [\text{height (m)}]^2$.

BMI will be measured and recorded at Screening. A subject will be excluded if BMI is $\leq 18 \text{ kg/m}^2$ or $\geq 32 \text{ kg/m}^2$, or weight $\leq 100 \text{ lbs}$ at Screening.

Body weight only (i.e., not including height or recalculation of BMI) will also be measured on Day-1

- **Vital Signs (VS):** Include body temperature (oral), BP (resting more than 5 min), RR, and HR. Heart rate and BP will be measured at rest with the participant supine for at least 5 minutes.¹. Repeat measurements with the participant supine may be allowed if the first measurement is abnormal (See [Section 8.1.4](#))

Note 1: Orthostatic blood pressure and heart rate will be obtained and recorded after the supine VS, while a participant is in standing position with measurements taken at 1 minute \pm 15 seconds and 3 minutes \pm 15 seconds after standing.

VS will be measured before any blood draws at the Screening Visit and Check-in (Day -1).

- **Electrocardiogram (ECG):** Standard twelve-lead ECG using an ECG machine that automatically calculates the HR and measures PR interval, RR interval, QRS interval, QT interval, and QT interval corrected by the Fridericia (QTcF) formula. QTcF may also be calculated manually by the site. Participants should be in a supine position and should have an approximate 10-minute rest period prior to the test. ECGs will be recorded before any blood draws.

The ECGs will be reviewed by the PI or authorized sub-investigator or study clinician (listed on FDA Form 1572) for ECG interval and for morphologic abnormalities. If a question regarding ECG interpretation arises, the study investigators will have the ECG reviewed by a cardiologist. To be eligible for participation, the PR and QTcF interval must be within protocol reference range criteria (as shown in [Appendix A](#)) at Screening and Check-in (Day -1) and there must be no clinically significant ECG abnormalities.

- ECGs will be obtained at the Screening Visit and Check-in (Day -1).

